Hypoglycaemia in subjects suffering from type 2 diabetes may have substantial consequences including a significant negative impact on quality of life [1], [2]. Further, repeated minor hypoglycaemias may result in significant productivity losses. In healthy subjects a number of studies show that during a hypoglycaemic episode with plasma levels of 2.2 – 2.5 mmol/L (40-45 mg/dl) brain areas responsible for cognition have an altered neuronal function when measuring cerebral blood flow [3], [4]. This is accompanied by severely impaired cognitive function with a reduced ability to solve simple cognitive tasks. At higher levels of glucose (above 3 mmol/L (54 mg/dl)), it remains to be settled whether cognitive functions are also affected negatively and whether this may be accompanied by changes in brain metabolism. Apart from raising the blood glucose directly or indirectly via glucagon, no treatment for hypoglycaemia exists, but since GLP-1 based therapies used in type 2 diabetes may affect brain glucose consumption, therapeutic interventions to prevent negative results of hypoglycaemia may eventually become clinically possible [5].

Here, we propose to provide quantitative results on cognition during an acute mild hypoglycaemic episode (target plasma glucose 3 mmol/L). Data will be provided on executive function, attention and memory.

Objectives and endpoints

Objective

To investigate our hypothesis that acute mild hypoglycaemia in patients with diabetes type 2 volunteers is associated with cognitive impairment of executive function, attention and memory.

Primary endpoint

- Performance on the Symbol Digit Modalities Test (SDMT)

Secondary endpoints

- Additional measures of executive function, attention and memory (see section on neurocognitive tests).

Hypothesis

- Mild hypoglycaemia attenuates cognitive performance in type 2 diabetes.

[figure not shown]
Study design

Our study is a randomised, single-centre, single-blinded, two-period cross-over trial in subjects with type 2 diabetes examining the effect of an acute hypoglycaemic episode on cognitive function.

Each subject undergoes two experimental days in randomized order with a 21-42 day interval, Day A and Day B. At each visit they will undergo a clamp procedure where their plasma glucose levels will be clamped at either a hypoglycaemic (PG < 3.1 mmol/L, goal during clamp 2,8-3,2) or at an euglycaemic level (6 mmol/L, goal during clamp 5,8- 6,2). During the two conditions (hypoglycaemia or euglycaemia) cognitive performance will be assessed by validated cognitive tests.

The trial consists of a screening visit (Day 0) 2-35 days prior to two following experimental visits (Day A and B), that will be separated by a period of 21-42 days during which the participants will resume their normal medical and lifestyle treatments.

An information visit prior the screening visit and a phone call follow-up after completion of the second experimental day are included in the trial as well.

Participants

Participant Selection

Number of participants: Based on previous studies and the following power calculation, we estimate that a study will be informative with 28 participants.

Inclusion criteria:

- Informed and written consent
- Clinically diagnosed type 2 diabetes mellitus for at least 3 months (diagnosed according to the criteria of the World Health Organization (WHO)).
- Normal haemoglobin ≥ 8.0 mmol/L (male) or ≥ 6.4 mmol/L (female)
- Male or female participants aged 35-70 years, both inclusive.
- Treated with diet or any antidiabetic medication except sulfonylureas, meglitinides or insulin.
- HbA1c ≤ 9.0 % by local laboratory analysis.
- BMI >23 kg/m² and <35 kg/m²

Exclusion criteria:

- Receipt of any investigational medicinal product within 3 months before screening in this trial.
- Liver disease (alanine aminotransferase (ALAT) and/or serum aspartate aminotransferase (ASAT) >2 times normal values) or history of hepatobiliary disorder.
- Nephropathy (serum creatinine levels ≥ 126 $\mu\text{mol/L}$ (male) or ≥ 111 $\mu\text{mol/L}$ (female)).
- Cardiac problems defined as decompensated heart failure (New York Heart Association (NYHA) class III and IV) at any time and/or angina pectoris within the last 12 months and/or acute myocardial infarction at any time.
- Active or recent malignant disease.
- Treatment with drugs that cannot be paused for 12 hours.
- Repeated resting blood pressure at screening outside the range 90–140 mmHg for systolic or 50–90 mmHg for diastolic. This exclusion criterion also pertains to subjects taking antihypertensives.
- Visual impairment or auditory impairment.
- Known abnormalities of the central nervous system or any endocrinological (with the exception of diabetes mellitus and euthyroid goiter), haematological, neurological, psychiatric diseases or other major disorders that in the opinion of the investigator precludes compliance with the protocol, evaluation of the results or represent an unacceptable risk for the participant's safety.
- Proliferative retinopathy (funduscopy performed within 3 months before the screening is acceptable) and/or severe neuropathy.
- Current treatment with systemic drugs, which may interfere with glucose metabolism.
- Significant history of alcoholism or drug/chemical abuse as per investigator's judgement.
- Current tobacco user (smoking or nicotinic product use 3 months prior to screening).
- Severe hypoglycaemic event during the past 6 months.
- Known hypoglycaemia unawareness.
- Participants with mental incapacity or language barriers precluding adequate understanding or co-operation or who, in the opinion of the investigator or their general practitioner, should not participate in the trial.
- For females only: Pregnancy, breast-feeding status or intention of becoming pregnant during the trial.
- Any chronic disorder or severe disease that in the opinion of the investigator might endanger participant's safety or compliance with the protocol.

Methods

This trial consists of a screening visit (Day 0) followed by two experimental days (Day A and B) with procedures as explained below.

Information visit

Prior to any protocol-related procedures, an information visit is arranged where potential participants will be provided with oral and written information about the trial and all the procedures involved. At this visit the medical doctor responsible for the project explains about the project in undisturbed and confidential surroundings. A suitable room for this is available at the Department of Endocrinology at Bispebjerg Hospital. The potential participant will prior to the information visit be informed about the possibility of bringing an assessor. Subjects will be offered a period of one week for consideration before deciding on

participation. If the person immediately decides to participate, written consent is obtained and screening subsequently performed.

Screening visit (Day 0)

The screening visit will take place 2-35 days prior to the first experimental day (Day A). The signed and dated informed consent is assessed and inclusion and exclusion criteria are checked. Demography (date of birth, ethnicity, sex) is assessed along with current medication and medical history are recorded. Height, weight, body mass index (BMI) and blood samples (creatinine, electrolytes (Na⁺, K⁺, Ca), ALAT/ASAT, alkaline phosphatase, albumin, bilirubin, haemoglobin, plasma glucose, C-reactive protein (CRP), HbA_{1c}, coagulation tests (INR and coagulation factor II, VII and X). Date of the diabetes diagnosis and current diabetes treatment is obtained, and finally a physical examination is performed and vital signs and an ECG will be assessed.

On the basis of the screening results, eligible participants are included in the study, and dates for the two experimental days are planned.

Experimental days (Day A and B)

If a participant meets one or more of the following exclusion criteria on any of the experimental days (Day A and B), he or she will be excluded from the visit or withdrawn from the trial:

Exclusion criteria:

- Consumption of alcohol within 24 hours prior to an experimental day.
- Extensive physical exercise within 24 hours prior to an experimental visit that will interfere with trial results, as judged by the investigator.
- Any use of systemic drugs that may interfere with glucose metabolism.
- Hypoglycaemia (detected as a plasma glucose (PG) ≤ 3.9 mmol/L) within 48 hours prior to an experimental day.

Participants will be instructed to maintain a regular diet and avoid alcohol and excessive eating for 3 days before each experimental day.

Day A

Subjects arrive at the laboratory after an overnight (10 hours) fast (water, coffee, tobacco, medicine) having avoided strenuous physical activity from the day before. They are placed in a recumbent position and will have a cannula inserted into a cubital vein. Another cannula is inserted into a contralateral cubital vein for insulin and glucose infusions.

On the first experimental day a hyperinsulinaemic hypoglycemic clamp is performed. At time 0 minutes, insulin infusion is initiated (Actrapid, Novo Nordisk). Plasma glucose is measured bedside every 5 minutes, allowing the plasma glucose level to be clamped on 3 mmol/L using an adjustable continuous infusion of 20 % glucose. Neurocognitive testing is initiated when glucose levels have been stabilized for 40 minutes and lasts for approximately 45 minutes.

Day B

Hyperinsulinaemic hyperglycemic clamp. Equal to Day A except that the plasma glucose level is clamped on 6 mmol/L.

Blood specimens:

Blood will be drawn at 30 after goal PG is reached, into chilled tubes containing heparin for analyses of insulin, C-peptide, epinephrine, glucagon, cortisol and growth hormone. Plasma samples are stored at -20°C until analysis. For bedside measurements of plasma glucose, blood is added to fluoride tubes and centrifuged at room temperature immediately for 30 seconds at 7400g.

Analytical procedures:

Plasma glucose concentrations are measured by the glucose oxidase method. Plasma insulin and C-peptide concentrations are measured using a two-sided electrochemiluminescence immunoassay (Roche/Hitachi Modular Analytics; Roche Diagnostic GmbH).

Performance of Cognitive Tests:

Neurocognitive test battery:

The test battery includes the following neurocognitive tests: Rey Auditory Verbal Learning Test (RAVLT) [6] (verbal memory), Trail Making Test (TMT) [7] part A and B (psychomotor speed and executive function), Symbol Digit Modalities Test (SDMT) [8] (psychomotor speed and executive function), WAIS-III Letter-Number Sequencing test [9] (executive function), verbal fluency test (letters S and D) (executive function) and Rapid Visual Processing (RVP) test from the Cambridge Neuropsychological Test Automated Battery (CANTAB) (sustained attention) [10], [11]. To avoid learning effects from baseline to follow-up testing, we will use alternate versions of the tests that are associated with greatest learning effects (incl. the RAVLT). Verbal IQ is estimated with the Danish Adult Reading Test (DART) (equivalent to the National Adult Reading Test; NART). The total duration of neuropsychological testing on each occasion is approximately 45 min.

All experiments are carried out at the Department of Endocrinology, Bispebjerg University Hospital, [name], where the necessary equipment is available.

Randomisation procedure

The participants of this randomised single-blinded study will be treated in a randomized sequence; either hypoglycaemia followed by euglycaemia or euglycaemia followed by hypoglycaemia. The investigator will be blinded to the treatment sequence until randomisation of the participant.

Calculations and statistics

Data is processed and presented with the use of standard descriptive statistics. AUCs are calculated by use of the trapezoid rule. Repeated measurement analysis of variance is used for statistical analysis of repeated measurements in the same subject. Data that is not normally distributed is compared using the Mann-Whitney U-test.

A recent trial applying the cognitive DSST score (part of the above neurocognitive test battery) in type 1 diabetes revealed a standard deviation (*SD*) between eu- and hypoglycaemia of 9 [12]. We suggest a similar level of variance in this study and from previous trial opt to detect differences of 6 or more. *P* values ≤ 0.05 will be considered as statistically significant, i.e. significance level of 5%, which will allow a sample size of 28 to yield a more than 90% high chance of detecting a true difference in cognition.

Only data from trial participants who have completed the entire study will be included in the statistical analysis.

Side effects, risks and disadvantages for participants

The 10 hour fast prior to each research day is a part of the natural nocturnal fast (10 PM - 8 AM), and is neither associated with discomfort or danger.

Insulin when administered can lead to hypoglycaemic episodes. This will sometimes appear as certain symptoms like palpitations (increased heartbeat/pulse), hunger, tremor (slight shaking), pallor, nausea, headache, sudden perspiration, feelings of anxiety, visual and speech disorders, paraesthesia (tingling and numbness in the feet and hands), symptoms of paralysis, and unsteadiness. If the condition progresses to severe hypoglycaemia, it can lead to loss of self-control, unconsciousness and, in extreme cases, death.

The participants of this trial will be exposed to hypoglycaemia and they will be closely monitored during this procedure. During the development of hypoglycaemia a physician and at least one trained person should be monitoring the participant, while a second physician should be available in 1-2 minutes on-call. A glucose solution will be placed close to the participant as a safety precaution, and plasma glucose concentration must be monitored frequently during the hypoglycaemic episode. In general, mild to moderate hypoglycaemia (plasma glucose levels ≤ 3.9 mmol/L) can be treated by ingestion of carbohydrates, while severe hypoglycaemia should be treated by the investigator and with the best available medical practice (e.g. dextrose given intravenously, or glucagon given subcutaneously or intramuscularly).

As a theoretical complication associated with intravascular catheters (and any other penetration of the skin and blood vessels with sharp/pointed objects) superficial phlebitis should be mentioned. Superficial phlebitis is not dangerous and will be treated with antibiotics should any sign of infection be present. The risk of superficial phlebitis is small and minimized by compliance with clinical standards for the insertion of intravenous catheters including double cleansing of the skin with an ethanol swap and other sterile procedures.

Participants physical and mental integrity and privacy

Information regarding participants of the project will be protected in accordance with the applicable laws of Denmark. The protocol is reported to The Danish Data Protection Agency via the Capitol Region of Denmark.

Operating costs and economy

The responsible physician of the project is professor [name] from Department of Endocrinology, Bispebjerg University Hospital. The project is initiated by MD, PhD, [name] and funded by the pharmaceutical company MSD with DKK 1.4 million. Neither [name] nor the rest of the research group have any financial interests in the conduct and outcome of the project or the company funding the project.

In case of additional costs we plan to apply for funding from public and private funds. The Research Ethics Committee will be informed if additional funding is achieved. Funds will be deposited in an account administered by Bispebjerg University Hospital.

Remuneration and reimbursement of costs for trial participants

Documented travel expenses related to the project will be reimbursed. For the inconvenience and the time spent (two study days of approximately 8 hours and one screening visit of

around 1 hour), each participant will be remunerated DKK 1200 (taxable income). If participants choose to withdraw prematurely from the study they will be reimbursed according to the time spent (DKK 600 per study day).

Availability of data for participants

All participants are guaranteed access to more information about the project.

Publication of study results

Data from the study will be processed and presented in one or more manuscripts for publication in international scientific journals. Inconclusive, negative and positive test results will be published, in accordance with the law concerning processing of personal data.

Adjournment of trial

The experiment is ended for each participant in case they wish to withdraw from the protocol, or in case exceptional circumstances make it impossible to complete the study. Likewise, any extraordinary event that makes it impossible to finish the project will result in termination of remaining study days. In any case of premature termination, the participants will be informed about the decision and the reason why.

Recruitment of participants

Patients with type 2 diabetes will be recruited among persons who have previously participated in trials and at that time accepted to be contacted again regarding other research projects, or among the patients attending the out-patient diabetes clinic in Department of Endocrinology at Bispebjerg Hospital. Alternatively, participants will be recruited through advertising in newspapers or on websites such as www.forsoegspersoner.dk. Potential participants will be contacted by telephone or email, except for patients attending the out-patient diabetes clinic, where the first contact will be in writing with an approved contact letter.

Exposition to the National Health Research Ethics Committee

All participants receive oral and written information, and oral and written consents are obtained prior to any protocol activity. A doctor who is not otherwise in charge of their treatment (if any) informs participants. The protocol is in compliance with the principles of Helsinki Declaration II.

All participants are assigned with a trial number and will on datasheets and tubes only appear with initials and trial number. The full name, social security number and trial number will be stored separately. If necessary, participants are covered by the patient insurance of Bispebjerg Hospital.

Participants are fully informed about possible adverse events and inconveniences related to trial procedures, and adequate precautions have been implemented in the study design in order to minimise the risks of participating in the trial.

Blood samples (100 ml per participant) will be stored at our department in a research biobank until analysis and completion of the study. Any excess plasma, blood and white blood cells will be stored at our department for up to 10 years after the completion of the study. In case of any re-analyses or need for further analyses a new approval by the National Health Research Ethics Committee is required.

The project will not benefit the individual participant (apart from the general medical examination, which is part of the screening visit), but it will add valuable information to our understanding of hypoglycaemia. Perhaps such knowledge can lead to new and improved strategies in the treatment of type 2 diabetes.

Bibliography

- [1] “Nocturnal hypoglycaemia: clinical manifestations and therapeutic strategies toward prevention,” *Endocr. Pract.*, vol. 9, no. 6, pp. 530–543, Nov. 2003.
- [2] D. Wild, R. von Maltzahn, E. Brohan, T. Christensen, P. Clauson, and L. Gonder-Frederick, “A critical review of the literature on fear of hypoglycaemia in diabetes: Implications for diabetes management and patient education,” *Patient Educ. Couns.*, vol. 68, no. 1, pp. 10–15, Sep. 2007.
- [3] L. G. Bie-Olsen, T. W. Kjaer, U. Pedersen-Bjergaard, M. N. Lonsdale, J. J. Holst, I. Law, and B. Thorsteinsson, “Changes of cognition and regional cerebral activity during acute hypoglycaemia in normal subjects: A H215O positron emission tomographic study,” *J. Neurosci. Res.*, vol. 87, no. 8, pp. 1922–1928, Jun. 2009.
- [4] J. M. Rosenthal, S. A. Amiel, L. Yáguez, E. Bullmore, D. Hopkins, M. Evans, A. Pernet, H. Reid, V. Giampietro, C. M. Andrew, J. Suckling, A. Simmons, and S. C. R. Williams, “The Effect of Acute Hypoglycaemia on Brain Function and Activation A Functional Magnetic Resonance Imaging Study,” *Diabetes*, vol. 50, no. 7, pp. 1618–1626, Jul. 2001.

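### The design text randomises the order of the two clamps, but the Day A procedure fixes hypoglycaemia on the first experimental day

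*Combined protocol and SAP*

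**What the plan says.** The design text is clear that order is randomised. The Study design section calls the study a "randomised, single-centre, single-blinded, two-period cross-over trial in subjects with type 2 diabetes" and adds: "Each subject undergoes two experimental days in randomized order with a 21-42 day interval, Day A and Day B". It then says that the clamp at each visit may be at either level. The Randomisation procedure section names both sequences: "either hypoglycaemia followed by euglycaemia or euglycaemia followed by hypoglycaemia".

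The procedures text differs. The Screening visit (Day 0) section gives Day A a calendar meaning: "The screening visit will take place 2-35 days prior to the first experimental day (Day A"). The Day A procedure then assigns a clamp to that day: "On the first experimental day a hyperinsulinaemic hypoglycemic clamp is performed". The Day B entry reads: "Hyperinsulinaemic hyperglycemic clamp. Equal to Day A except that the plasma glucose level is clamped on 6 mmol/L". Nothing in these sections makes the clamp level depend on the allocated sequence.

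On learning effects, the Neurocognitive test battery section says "we will use alternate versions of the tests that are associated with greatest learning effects (incl. the RAVLT"). The primary endpoint, the SDMT, is not named there, and the list is open.

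**The concern.** Day A and Day B do two jobs. In the Study design section they are the items being put in random order, so they act as condition labels. In the Screening visit section Day A is the first visit, so it is a calendar label. The Day A procedure joins the two and places hypoglycaemia first for everyone.

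The order of the clamps is what protects the primary comparison from practice effects. If the procedure were followed as written, condition and visit would coincide completely. Better SDMT performance at the second visit through familiarity would look the same as impairment under hypoglycaemia, and it would push the result towards the trial's hypothesis. The protocol itself expects learning effects. Its safeguard, alternate test versions, cannot be assumed to cover the SDMT.

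**Working it through.** **1. Can one reading reconcile the sections?**

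- *Day A and Day B as condition labels, taken in random order.* This fits the Study design section. It fails on the Screening visit section, which equates Day A with the first experimental day. It also fails on the Day A procedure, which names the first experimental day outright and does not rely on the label. For a participant allocated euglycaemia first, the 2-35 day screening window would also attach to the second visit if it followed the Day A label.
- *Day A and Day B as calendar labels.* This fits the Screening visit section and the Day A procedure. Every participant then has hypoglycaemia first, which contradicts both the Study design and the Randomisation procedure sections.

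No single reading fits all the sections. The contradiction is textual and needs no calculation. The arithmetic below shows only what depends on it.

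**2. The plan's own power figure.** Inputs from Calculations and statistics: n = 28, difference 6, SD 9 between conditions (read as the SD of the within-subject difference), significance level 5%. Sidedness is not stated, so two-sided is assumed.

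- Standard error = 9/√28 = 1.701, and 6/1.701 = 3.528.
- Normal approximation: Φ(3.528 − 1.960) = 94.2%.
- Exact paired t-test (non-central t, 27 df): 92.5%.
- Period-adjusted cross-over analysis, assuming 14 per sequence (26 df): 92.4%.

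The stated power of more than 90% is reproduced, and it holds with randomised order.

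**3. Practice effect under randomised order.** Let π be the gain at the second visit. With n₁ participants having hypoglycaemia first and n₂ having it second, the unadjusted mean difference carries a bias of π(n₁ − n₂)/28 towards impairment.

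- At 14:14 (assumed; the protocol gives no allocation ratio) the bias is π × 0/28 = 0. In simulation (200,000 runs, SD 9, π from 0 to 5) the unadjusted paired t-test rejects in 5.0% of runs, falling to 2.5%. A period-adjusted test rejects in 4.9–5.0%.
- Under simple 1:1 randomisation (also assumed) the expected bias is zero and the simulated false-positive rate is about 5%. A chance imbalance can leave a little in one trial: at 16:12 and π = 3, 3 × 4/28 = 0.43 points.

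**4. Practice effect if the Day A procedure is followed literally.** Now n₁ = 28 and n₂ = 0, so the bias is π × 28/28 = π. With no true effect, the chance of a significant two-sided paired t-test comes from the non-central t with 27 df, critical value 2.052 and non-centrality (π/SD)√28. For π = 3 and SD 9 the non-centrality is (3/9) × 5.292 = 1.764.

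| Assumed practice gain (points) | SD 7 (assumed) | SD 9 (protocol) | SD 11 (assumed) |
|---|---|---|---|
| 0 | 5.0% | 5.0% | 5.0% |
| 1 | 11.3% | 8.8% | 7.5% |
| 2 | 30.8% | 20.5% | 15.3% |
| 3 | 59.0% | 39.8% | 28.5% |
| 4 | 83.0% | 62.1% | 45.9% |
| 5 | 95.4% | 80.9% | 64.0% |

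The documents give no practice gain, so the rows are an assumed range. The SD of 9 is borrowed: "A recent trial applying the cognitive DSST score (part of the above neurocognitive test battery) in type 1 diabetes revealed a standard deviation" of that size. It therefore comes from a different test and a different population from the SDMT in type 2 diabetes, which is why 7 and 11 are shown beside it. The plan names repeated-measures analysis of variance. With two conditions and no period term, that is equivalent to the paired t-test used here.

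**The case against.** The strongest reply is that the intent is not in doubt. The design description, the statement of randomised order and the Randomisation procedure section all agree, and the last writes out both sequences. The Day A sentence is then a drafting slip. On the intended reading the expected practice bias is zero, and sample size, power and endpoint do not change. The percentages in the table need two things: staff who follow one sentence over the randomisation section, and practice gains that the documents do not supply. Nothing in the documents says which section staff would work from. The Screening visit section, taken alone, assigns no clamp; only the Day A procedure does.

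Most of this stands, and it limits the weight of the point. The table illustrates a misreading and does not describe the plan as intended. An exact 14:14 split is an assumption; under simple 1:1 randomisation it would occur with probability of about 15%, and the expected bias would still be zero.

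The reply does not remove the contradiction. The conflicting sentence is in the Methods, where the procedures for each day are set out. The Randomisation procedure section does not say how the allocated sequence determines the clamp on a given day. A clear intent elsewhere makes the error easy to correct, but the text still gives opposite instructions for anyone allocated euglycaemia first.

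**Conclusion.** The inconsistency is real and should be fixed. The order is randomised in the design and randomisation text, and fixed with hypoglycaemia first in the Day A procedure. It is very probably a drafting error, and nothing here shows that a fixed order was used.

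If the order is randomised as intended, the expected practice bias is zero and the false-positive rate stays at or below about 5%. If the procedure is followed literally, the bias equals the whole practice gain and cannot be removed by analysis. With the protocol's SD of 9, the false-positive rate would then run from 9% at an assumed 1 point to 81% at an assumed 5 points. These figures rest on n = 28, a two-sided paired test at 5%, no true effect, and practice gains that are assumptions. The finding of a contradiction rests on none of them.

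**What to change.** Reconcile the Study design, Screening visit, Day A / Day B and Randomisation procedure sections:

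- Use Visit 1 and Visit 2 for the calendar, and separate names for the two clamp conditions (3 mmol/L clamp, 6 mmol/L clamp). Retire Day A and Day B as dual-purpose labels.
- State in the Methods that the condition at each visit follows the participant's randomised sequence, and remove the wording that ties the hypoglycaemic clamp to the first experimental day.
- Tie the 2-35 day screening window to Visit 1.

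Two smaller points can be settled in the same edit. State whether the SDMT is among the tests given in alternate versions. Use one name for the 6 mmol/L condition, which is called euglycaemic in the Study design section and hyperglycaemic under Day B.

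The cost is a wording amendment to the Methods. Patient numbers, power and resources do not change.

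### The plan leaves open whether the primary SDMT gets alternate forms and describes no practice run, so learning that differs by sequence could dilute the primary contrast

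*Combined protocol and SAP*

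**What the plan says.** The study design section describes a "randomised, single-centre, single-blinded, two-period cross-over trial in subjects with type 2 diabetes". On timing it states: "Each subject undergoes two experimental days in randomized order with a 21-42 day interval, Day A and Day B". The primary endpoint is "Performance on the Symbol Digit Modalities Test (SDMT").

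The neurocognitive test battery section recognises learning as a threat. The stated purpose is "To avoid learning effects from baseline to follow-up testing", and the measure is that "we will use alternate versions of the tests that are associated with greatest learning effects (incl. the RAVLT"). The set of tests is not listed beyond that example, and nothing is said about how forms would be distributed over conditions or periods.

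The screening section covers consent, eligibility, history, medication, anthropometry and blood samples, and closes its list with "finally a physical examination is performed and vital signs and an ECG will be assessed". It then says "On the basis of the screening results, eligible participants are included in the study". No cognitive test or familiarisation appears there, or on either experimental day before the scored battery.

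The calculations and statistics section names repeated-measures analysis of variance and the Mann-Whitney U-test. It specifies no period, sequence or carry-over term.

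**The concern.** Because no cognitive baseline is scheduled, the first exposure to the SDMT is itself a scored primary measurement under one of the two conditions, and the second comes after that exposure. Any practice gain therefore lies inside the comparison.

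A cross-over handles such a gain well only if it is the same whichever condition came first. There is some reason to ask whether it would be. The objective is to test whether acute mild hypoglycaemia "is associated with cognitive impairment of executive function, attention and memory". If a hypoglycaemic first session also leaves behind less learning of the symbol key or of how to tackle the task, those participants would gain less at their second visit than participants who started under euglycaemia. That is carry-over that differs by sequence.

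At stake is a diluted estimate. A small or null result could be read as absence of impairment near 3 mmol/L, the question that the introduction calls unsettled.

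**Working it through.** **Inputs.** From the calculations and statistics section: difference to detect 6, SD 9 (read as the SD of the within-person difference), significance level 5%, 28 participants, power stated as more than 90%. Assumed because not stated: a two-sided test and 14 participants per sequence. No SDMT practice gain or retention figure is given, so the gaps below are assumptions.

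**Step 1: the plan's own figure.** Paired t-test with 27 degrees of freedom: noncentrality = (6/9) × √28 = 3.53, critical value 2.05, power 92.5%. With a period term (26 degrees of freedom) it is 92.4%. The normal approximation, Φ(3.53 − 1.96), gives 94.2%. The stated power reproduces.

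**Step 2: what learning does to the contrast.** Let d be the true euglycaemia-minus-hypoglycaemia difference, and let pE and pH be the gains at the second visit after a euglycaemic and a hypoglycaemic first visit.

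- Hypoglycaemia first: the expected within-person difference is d + pH.
- Euglycaemia first: the expected within-person difference is d − pE.
- Average over equal sequences: [(d + pH) + (d − pE)]/2 = d − (pE − pH)/2.

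If pE = pH, the second term is zero and there is no bias. If pE exceeds pH, the estimate falls by half the gap. A period term leaves this average unchanged.

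**Step 3: size under assumed gaps.** Noncentrality = (6 − gap/2)/9 × √28, with 27 degrees of freedom.

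| Assumed gap pE − pH | Expected contrast | Power |
|---|---|---|
| 0 | 6.00 | 92.5% |
| 0.5 | 5.75 | 90.3% |
| 0.6 | 5.70 | 89.8% |
| 1 | 5.50 | 87.6% |
| 2 | 5.00 | 80.9% |
| 4 | 4.00 | 62.1% |

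Power drops below the stated 90% at a gap of between 0.5 and 0.6 points. Fitting a period term (26 degrees of freedom) changes these values by about 0.1 percentage point.

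**Step 4: equal learning, for comparison.** Equal gains of 2, 4 and 6 points in both sequences cause no bias. If no period term is fitted they only add noise: simulated power is 92%, 89% and 85%.

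**Step 5: could a carry-over test find the problem later?** The test compares each person's two-period total between sequences; the expected difference is pE − pH. With an assumed within-person correlation r, the per-period variance is 81/[2(1 − r)] and the SD of the total is √[2 × variance × (1 + r)]. For r = 0.5, 0.7 and 0.8 this SD is 15.6, 21.4 and 27.0. With 14 per sequence, power for gaps of 2 to 6 points is about 5% to 17%. The data could not reliably show the problem, so prevention by design is the practical route.

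**The case against.** The strongest reply is that randomised order already deals with the main practice-effect worry. That is right: ordinary learning, equal in both sequences, cancels. Only the gap between sequences matters, and it enters at half its size.

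Second, a reader might infer that alternate forms are reserved for the RAVLT. The text does not say that. The RAVLT is given as an example from a wider, unlisted set, and the SDMT may already belong to it. Likewise, the reference to baseline and follow-up may just be loose wording for first and second test, and does not show that the safeguard fails to apply.

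Third, a reader might infer that SDMT learning is known to persist over 21-42 days, or that the trial's memory hypothesis by itself implies dilution. Neither is supported. No retest figure is given. The hypothesis concerns performance during hypoglycaemia, not what is retained weeks later, and the battery section classes the SDMT under psychomotor speed and executive function while assigning verbal memory to the RAVLT. Memory could be impaired during the clamp with pE − pH close to zero on the SDMT.

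Fourth, the size may be small. At a gap of 0.5 the stated power survives. If the gain after a hypoglycaemic visit is not negative, a gap of 4 requires a euglycaemic gain of at least 4 points, two thirds of the planned difference.

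All of this stands, and it limits the point to a possible bias of unknown size. It does not remove the point: protection of the primary endpoint is left unspecified, and a gap, if present, could not be removed by a period term.

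**Conclusion.** The point holds as a conditional weakness with a cheap remedy. The documents establish that the SDMT is the primary endpoint, that its form is unspecified, that no practice run is described, and that the first SDMT is therefore a primary measurement. Dilution by (pE − pH)/2 follows by algebra, given equal sequence sizes. Whether a gap exists, and how large it is, cannot be learned from the documents. The loss ranges from negligible below about half a point to roughly 30 percentage points of power at an assumed gap of 4 (92.5% − 62.1% = 30.4).

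Under the mechanism considered, the bias is toward no effect. A reader might infer that learning could manufacture the hypothesised impairment; with pE larger than pH and randomised, balanced order, it would not. That reassurance depends on the order really being randomised. The Day A description places the hypoglycaemic clamp on the first experimental day, which conflicts with the randomisation section and must be reconciled.

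The stated sample size and power reproduce, and no figure needs correcting on this account.

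**What to change.** 1. Add one unscored SDMT familiarisation at the existing screening visit (Day 0), using a separate form or practice key that is not used on the experimental days. The aim is for early learning to take place before the first randomised measurement.
2. State that the SDMT is among the tests given in alternate forms, list the others, and counterbalance the two SDMT forms within each randomised sequence so that form is confounded with neither condition nor period.

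The cost is a sentence or two in the protocol, extra test sheets, a few minutes added to a screening visit of about one hour, and a possible small form-to-form difference, which counterbalancing is meant to handle. No visit or participant is added.

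The limits should be acknowledged. Alternate forms address learning of the key but not of test strategy. The practice run may reduce unequal learning, but these documents cannot show that it would eliminate it. Enlarging the trial is a poor substitute: with a period term, 90% power would need 32, 38 or 56 participants at gaps of 1, 2 or 4 points, and the estimate would remain diluted.
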